6.4 Exploratory Immunogenicity Endpoints

Predicted vaccine efficacy (PVE) and associated 95% CI will be calculated at Day 64 and Day 29 for the combined AV7909 groups using efficacy data from Emergent's nonhuman primates GLP [Study 3655-100072763](#) and the observed TNA values in this clinical study. The computational algorithm with double-bootstrap method to calculate confidence intervals proposed by Kohberger ([Kohberger, 2007](#)) will be used. The details are provided in [Appendix II](#).

6.5 Subgroup Analyses for Immunogenicity

Subgroup analyses of immunogenicity data will be tabulated by age group, sex, and race as described in [Section 4.6](#) in the similar manner as specified in [Section 6.1](#). Line plots of estimated GMT with associated 95% CI for TNA NF₅₀ over time by subgroup variable and treatment group will be provided.

7 SAFETY ANALYSIS

All safety data will be presented based on the Safety Population. Data summaries will be tabulated by two treatment groups, AV7909 (three lots pooled) and BioThrax group. Continuous variables will be summarized using number of participants (n), mean, SD, median, minimum, and maximum; categorical variables will be summarized by the number (frequency) and percentage in each category.

7.1 Exposure to Study Drugs

Exposure will be tabulated as the numbers and percentages of participants by vaccination and treatment group (AV7909 and BioThrax) for all vaccinations administered and for per-protocol vaccinations. Per-protocol vaccinations include vaccinations administered without any administration issues, eg, incorrect product administered, incorrect dose of IP, incorrect route, missing previous dose, and outside the acceptable visit windows on Days 1 (NA), 15(± 1) and 29(± 2). The data listing including date and time of IP administration and injection location (left or right arm) will be provided.

7.2 Adverse Events

All adverse events will be coded to system organ class (SOC) and preferred term (PT) according to the Medical Dictionary for Regulatory Activities (MedDRA) version 22.0.

7.2.1 Overall Summary of TEAEs

A treatment-emergent adverse event (TEAE) is defined as an AE that presents after the initiation of treatment or any AEs already present that worsen in either intensity or frequency following treatment. For programming purpose, any AEs with start date on or after the start date of the first vaccination will be counted as treatment-emergent. AEs with missing start dates, but with end dates later than the date of first vaccination will also be counted as treatment emergent.

An overall summary table with the following TEAE categories will be provided:

- TEAEs
- Vaccine-related TEAEs
- Grade 3 or 4 TEAEs
- Vaccine-related Grade 3 or higher TEAEs
- Serious TEAEs
- Serious vaccine-related TEAEs
- Death
- TEAEs leading to discontinuation of vaccination
- TEAEs leading to study withdrawal
- AESIs
- Vaccine-related AESIs

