9.2. Eliciting and Reporting Adverse Events

AEs (including SAEs and potential AESIs) reported spontaneously by the participant and/or in response to an open question from the PI or designee or revealed by observation (eg, during PE or from a clinical test result) will be recorded by the PI or designee on the AE eCRF if they

occurred from the time of the first vaccination on Day 1 up to Month 13, regardless of causal association with the IP. AE reporting is required for any new observation presenting after the first vaccination or for a deterioration of baseline condition (eg, increased severity/frequency). From the signing of the ICF until immediately before the first vaccination on Day 1, only AEs resulting from a study-related procedure will be recorded on the AE eCRF; all other events reported in this time period will be recorded as signs and symptoms on the Medical History eCRF. If there is any doubt as to whether a clinical or laboratory observation is an AE, the event will be considered an AE and recorded on the AE eCRF.

Refer to the specific sections on clinical laboratory tests ([Section 8.3.2](#)), PEs ([Section 8.3.3](#)), vital signs ([Section 8.3.4](#)), and e-diary reactogenicity ([Section 8.3.5.1](#)) for details on AE reporting based on participant observation and clinical test results.

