2.2.3.1 Adverse Events

AEs (including SAEs and potential AESIs) will be recorded on the AE eCRF by the PI or designee if they occurred from the time of the first vaccination on Day 1 up to Month 13, regardless of causal association with the investigational product (IP). AE reporting is required for any new observation presenting after the first vaccination or for a deterioration of baseline condition (i.e., increased severity/frequency). From the signing of the ICF until immediately before the first vaccination on Day 1, only AEs resulting from a study-related procedure will be recorded on the AE eCRF; all other events reported in this time period will be recorded as signs and symptoms on the Medical History eCRF.

Refer to the specific sections in the Protocol EBS.AVA.212 on clinical laboratory tests ([Section 8.3.2](#)), PEs ([Section 8.3.3](#)), vital signs ([Section 8.3.4](#)), and e-diary reactogenicity ([Section 8.3.5.1](#)) for details on AE reporting based on participant observation and clinical test results.

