3.4 Definition of Baseline

For all analyses, the baseline value is defined as the last non-missing value prior to the date and time of the first vaccination.

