7.2.2 All TEAEs

All TEAEs will be summarized by SOC and PT in descending order of participant incidence in AV7909 group (three lots pooled).

TEAEs that occurred in 1% or more for a PT term in either AV7909 group or BioThrax group will be tabulated by SOC and PT.

All TEAEs will be summarized by severity to IP, SOC, and PT for AV7909 (three lots pooled) and BioThrax group. All TEAEs will be summarized by relationship to IP, SOC, and PT for AV7909 (three lots pooled) and BioThrax group. Participants having the same TEAE more than once will be counted once for each PT and once within each SOC at the maximum severity and relatedness. If the severity/relatedness is missing for one or more of the occurrences, the maximum severity/relatedness of the remaining occurrences will be used.

For the analysis purpose of one of the secondary safety endpoints, the incidences of AEs from the time of the first vaccination on Day 1 through Day 64, where so indicated, selected

AE summaries will be provided for all TEAEs and for TEAEs reported during study period Day 1 to Day 64, respectively.

A participant data listing of all AEs (including treatment-emergent AEs (TEAEs) and non-TEAEs) sorted by site, study group, subject ID and AE start date/time will be provided. This listing will include a “Treatment-emergent” flag. Separate listing will be provided for Grade 3 or 4 TEAEs.

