All adverse events experienced during the study period in both enrollments will be included in the summary tabulations. All AEs on or after the start date of treatment in the first enrollment will be considered as treatment emergent. It is worth noting that AEs may be reported under both subject numbers, but this will not impact incidence tables when the verbatim terms provided at the individual sites code to the same preferred term.

ADCM

All medications taken during the study period in both enrollments will be included in the summary tabulations. Prior medications will be those taken 30 days prior to start date of the first treatment associated with the first enrollment while concomitant medications will be those taken on or after the start date of the first treatment during the first enrollment. Note that medications can be reported under both subject numbers, but this will not impact incidence tables when the reported medications provided at the individual sites are coded to the same preferred name.

ADMH

Medical history data reported for either subject number will be included in summary tabulation unless the start date for the second enrollment clearly identifies that the history began after the first treatment of the first enrollment. An analysis flag will be added to flag only medical history which can contribute to the analysis.

ADDV

All protocol deviations experienced during the study period associated with either enrollment will be included in the summary tabulations.

ADSS

Refer to Population indicator variables in ADSL.

ADDD, ADIE

No impact on analysis.

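### The SAP's treatment-emergent flag compares calendar dates only, so procedure-related AEs that start on Day 1 before the first injection are counted as TEAEs

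*SAP*

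**What the plan says.** - **Definition (SAP 7.2.1; same concept in Protocol 10.6.2).** A TEAE is "an AE that presents after the initiation of treatment or any AEs already present that worsen in either intensity or frequency following treatment".
- **Programming rule (SAP 7.2.1).** The next sentence turns this into code: "any AEs with start date on or after the start date of the first vaccination will be counted as treatment-emergent". It has no time of day and no pre-dose exclusion.
- **Duplicate enrolments (SAP Appendix IV, ADAE).** The same logic is used for the four people who enrolled twice: "All AEs on or after the start date of treatment in the first enrollment will be considered as treatment emergent".
- **What reaches the AE eCRF before dosing (SAP 2.2.3.1; Protocol 9.2).** From consent until "immediately before the first vaccination on Day 1, only AEs resulting from a study-related procedure will be recorded on the AE eCRF". Other events in that period go to the Medical History eCRF.
- **Endpoint window (SAP 2.3.2).** The secondary AE endpoint runs from the time of the first vaccination through Day 64.
- **Day 1 elsewhere in the SAP.** Baseline (SAP 3.4) is "the last non-missing value prior to the date and time of the first vaccination". Table 3 (SAP 3.3) splits Day 1 into a part before and a part after the first injection.
- **Times held.** The protocol has the time of each vaccination recorded (Section 6.4). The AE listing in SAP 7.2.2 is to be "sorted by site, study group, subject ID and AE start date/time will be provided".

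**The concern.** The definition turns on whether an event began before or after the first injection. The flag asks only whether it began on the same calendar day or later. The two questions differ on Day 1, when Protocol 8.1.2 schedules blood draws (TNA, RF, ANA, anti-dsDNA, TSH), vital signs and a symptom-directed examination ahead of the injection. A faint or an arm haematoma from the draw is an event that the plan requires on the AE eCRF, and vaccine not yet given cannot have caused it.

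At stake is whether the AE tables match their stated definition and the window of the secondary safety endpoint. No primary immunogenicity result is involved.

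**Working it through.** The plan states no figure on this point, so the check is mainly logical: apply the definition and the flag to each kind of event around the first dose.

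| Event | Where recorded | TEAE by definition? | Flagged by SAP 7.2.1? |
|---|---|---|---|
| Procedure-related, starts before Day 1 | AE eCRF | No | No |
| Procedure-related, starts on Day 1 before the injection | AE eCRF | No | **Yes** |
| Not procedure-related, starts on Day 1 before the injection | Medical History eCRF | No | Not in the AE data |
| Any AE that starts on Day 1 after the injection | AE eCRF | Yes | Yes |

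Only the second row conflicts. First vaccination must fall on the day of randomization (Protocol 4.1; SAP 4.3), so an AE from the Day 1 pre-dose draw carries the date of first vaccination.

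**Is there an overriding rule?**
- SAP 4.4 deals with missing and partial dates only.
- Table 3 in SAP 3.3 separates pre-dose from post-dose Day 1, but AEs are not among the data types it covers.
- SAP 3.4 uses date and time, but for baseline values.
- Appendix IV repeats the date-only test.

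No section of either document repairs the conflict.

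**Size.** The documents give no rate for Day 1 pre-dose procedure AEs. With an assumed proportion q, the number affected is N × q. The planned N is 3300 on AV7909 and 550 on BioThrax.

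| Assumed q | AV7909 (3300 × q) | BioThrax (550 × q) | Total (3850 × q) |
|---|---|---|---|
| 0.1% | 3.3 | 0.55 | 3.85 |
| 0.5% | 16.5 | 2.75 | 19.25 |
| 1% | 33 | 5.5 | 38.5 |
| 3% | 99 | 16.5 | 115.5 |

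The expected proportion is the same in both arms because the events precede exposure.

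**Effect on a between-arm difference.** Suppose the true any-TEAE risks are p_A and p_B, and a false event occurs independently with probability q. The observed risk in each arm is p + (1 − p)q = p(1 − q) + q. The observed difference is therefore (p_A − p_B)(1 − q). For an illustrative true difference of 5.0 percentage points, q = 3% gives 5.0 × 0.97 = 4.85 points, and q = 0.1% gives 5.0 × 0.999 = 4.995 points.

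**The case against.** The strongest case for leaving the rule alone has four parts.

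1. **It is an open and cautious convention.** The SAP presents it as a programming rule, and over-counting is the safe direction in a safety table. SAP 4.4 takes the same line for AEs with unknown dates. This stands as a reason for a date-only fallback when the time is missing. It does not justify ignoring a time that is held, and the SAP does not limit the rule to missing times.
2. **AE start time may not be reliably collected.** The eCRF is not in the documents. The only evidence is the sort order of the listing, and SAP 4.4 has no imputation rule for times. This stands as a condition on the fix.
3. **Some cases correct themselves.** In Protocol 8.1.2 the bloods are listed before the eligibility review and randomization. If a reaction to the draw postponed randomization to a later day, the AE date would precede vaccination and the date rule would classify it correctly. A minor bruise or brief faint need not postpone anything, so this narrows the problem without removing it.
4. **Little depends on it.** The tables affected are descriptive, and no safety hypothesis is tested. This stands, and it sets the priority of the point.

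**Conclusion.** The point holds as a minor inconsistency. For one kind of record that the plan requires, the flag contradicts the SAP's own definition and the start of the secondary endpoint window. The consequence is a small over-count, expected in equal proportion in both arms, in the any-TEAE and unrelated-TEAE tables. Its true size is unknown; the counts shown rest entirely on assumed rates. The relative risks for serious TEAEs (SAP 7.2.3) and AESIs (SAP 7.2.4) are unlikely to move materially: a reaction to a blood draw is seldom serious and would not be confirmed as autoimmune.

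A reader might infer more. The documents do not support these readings:

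- **That AEs which worsen after dosing are missed.** Protocol 9.2 and SAP 2.2.3.1 require a deterioration after the first vaccination to be reported as an AE. Reported that way, it has a post-dose start and is flagged. It would be lost only if a site amended the old record instead, and neither document describes that practice.
- **That the AV7909 versus BioThrax comparison is compromised.** Relative risks are planned only for serious TEAEs and AESIs. For all TEAEs, even a 3% rate shrinks a risk difference by only 3% of its value.
- **That the vaccine-related rows are inflated.** Under Protocol 9.2.2 the investigator rates causality, and an event before any injection should be rated unrelated.
- **That false events dominate terms such as presyncope or bruising.** The documents give no figure from which such a share could be worked out.

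**What to change.** In SAP 7.2.1, replace the date comparison with this rule: an AE is treatment-emergent if its start date/time is at or after the date/time of the first vaccination; where an AE starts on Day 1 and its start time is missing, it is counted as treatment-emergent, as now. Leave the existing rule for missing start dates unchanged. Make the same change in the ADAE paragraph of Appendix IV, so that the two places agree. Do not rely on a pre-vaccination marker on the eCRF, because neither document describes one.

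First confirm that the AE eCRF collects start time. If it does not, keep the date-only rule and state in SAP 7.2.1 and in a table footnote that Day 1 pre-dose procedure AEs are included.

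The cost is about one sentence in each of two places and a small change to the ADAE derivation. The rule does not depend on treatment arm and can be settled before unblinding. Nothing is lost from view: the AE listing in SAP 7.2.2 already covers AEs that are not treatment-emergent and carries a flag to tell them apart.

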7.2.2 All TEAEs

All TEAEs will be summarized by SOC and PT in descending order of participant incidence in AV7909 group (three lots pooled).

TEAEs that occurred in 1% or more for a PT term in either AV7909 group or BioThrax group will be tabulated by SOC and PT.

All TEAEs will be summarized by severity to IP, SOC, and PT for AV7909 (three lots pooled) and BioThrax group. All TEAEs will be summarized by relationship to IP, SOC, and PT for AV7909 (three lots pooled) and BioThrax group. Participants having the same TEAE more than once will be counted once for each PT and once within each SOC at the maximum severity and relatedness. If the severity/relatedness is missing for one or more of the occurrences, the maximum severity/relatedness of the remaining occurrences will be used.

For the analysis purpose of one of the secondary safety endpoints, the incidences of AEs from the time of the first vaccination on Day 1 through Day 64, where so indicated, selected

AE summaries will be provided for all TEAEs and for TEAEs reported during study period Day 1 to Day 64, respectively.

A participant data listing of all AEs (including treatment-emergent AEs (TEAEs) and non-TEAEs) sorted by site, study group, subject ID and AE start date/time will be provided. This listing will include a “Treatment-emergent” flag. Separate listing will be provided for Grade 3 or 4 TEAEs.

7.2.3 Serious TEAEs

Serious TEAEs will be summarized by SOC and PT. Serious TEAEs will be summarized by relationship to IP, SOC, and PT for AV7909 (three lots pooled) and BioThrax group as well.

A participant data listing of all serious AEs (both TEAEs and non-TEAEs) will be provided.

The safety outcome measure used for the primary safety analysis is the incidence rate of serious TEAEs. The within-group proportion of participants with serious TEAEs and associated two-sided 95% CI (exact Clopper-Pearson confidence limits) will be provided for AV7909 (three lots pooled) and BioThrax group. The relative risk (ratio of proportion of participants with serious TEAEs in AV7909 vs. BioThrax group) with exact unconditional 95% CI will be provided for treatment comparison between the two groups. No formal hypothesis testing will be conducted.

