2.3 Study Endpoints

2.3.1 Primary Endpoints

The primary study endpoints are as follows:

Lot Consistency:

- Equivalent immunogenicity across three consecutive AV7909 lots as demonstrated by the 95% confidence interval (CI) for the ratios of geometric mean TNA NF₅₀ at Day 64 for each of the three lot-to-lot comparisons to be within 0.5 and 2.0.
- Protective level of immunogenicity in all three consecutive AV7909 lots as demonstrated by the lower bound (LB) of the two-sided 95% CI to be $\geq 40\%$ for the proportions of AV7909 subjects in each of the three lots achieving a TNA NF₅₀ ≥ 0.56 at Day 64.

Both of the two lot consistency endpoints should be met to demonstrate AV7909 lot consistency.

Immunogenicity:

- Lower bound of the two-sided 95% CI is $\geq 40\%$ for the proportion of AV7909 participants in Groups 1-3 (three lots pooled) achieving a TNA NF₅₀ ≥ 0.56 on Day 64.
- Non-inferiority of AV7909 to BioThrax at Day 64 as determined by the two-sided lower 95% CI of the difference in the proportion of AV7909 participants (three lots pooled) with a TNA NF₅₀ ≥ 0.29 and the proportion of BioThrax participants with a TNA NF₅₀ ≥ 0.29 being greater than -15%.

Safety:

- Incidences of SAEs from the time of the first vaccination on Day 1 through the 12-month safety follow-up telephone call following the last vaccination.

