2.4 Sample Size and Power Considerations

Sample size for this study is based primarily on safety considerations. The total sample size across all three AV7909 study groups is set at 3300 participants. Allowing a 10% drop-out rate, this sample size for safety (3000) is sufficient to detect, with 95% probability, an AE rate of 1:1000, or 0.1%.

It is expected that more participants will be excluded from the immunogenicity analysis population (Per Protocol [PP] Population; refer to [Section 3.2](#)) than excluded from the Safety Population. A 25% exclusion rate from the PP Population is assumed. Thus, the PP Population will include approximately 800 participants for each AV7909 group (2400 participants total) and 400 participants for the BioThrax group.

Even under the best manufacturing practices, between-lot variation exists and will be considered normal. It is assumed that the lot-to-lot geometric mean titer (GMT) ratio could be as low as 0.6 based on Emergent's experience with the BioThrax vaccine. Conservatively, the largest GMT ratio between two out of three lots is assumed to be 1.5. Assuming a coefficient of variation of 100% (slightly larger than the observed 91% in the phase 2 study, EBS.AVA.208), this study has >99% power to demonstrate lot consistency with the pre-specified equivalence bounds ([0.5, 2.0]) in terms of GMT ratio for TNA NF₅₀ at Day 64.

Based on the combined phase 1 and phase 2 data, the proportion of participants receiving two doses of AV7909 on Day 1 and Day 15 with TNA NF₅₀ at Day 64 over 0.56 is approximately 63% with lower 95% CI of 50% (total n = 54). Even assuming a conservative 50%, the study provides >99% power of rejecting the null hypothesis of 40% in each of the three AV7909 lots and in the combined AV7909 group (three lots pooled).

For the non-inferiority endpoint, among participants (n = 184) receiving BioThrax PEP regimen (3 doses, SC) in the EBS.AVA.006 study, 93.5% had TNA NF₅₀ values above 0.29 at Day 64. In the AV7909 phase 2 study (EBS.AVA.208), 86.5% of participants (n = 37) had TNA NF₅₀ above 0.29 at Day 64. Assuming a rate of 93% for the BioThrax group and 83% for the AV7909 group, the sample sizes of 400 and 2400 provide approximately 98% power to demonstrate non-inferiority of the two-dose AV7909 IM regimen to the three-dose BioThrax SC regimen at Day 64 with a non-inferiority margin of 15%.

The sample size calculation was performed using PROC POWER in SAS/STAT 9.4.

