3.2 Analysis Populations

There will be three analysis populations for this study:

The Intent-to-treat (ITT) Population will include all participants who are randomized. Participants will be included in the study group to which they were randomized.

The Safety Population will include all randomized participants who receive at least one vaccination. Safety analyses will be based on the Safety Population according to the vaccine received (BioThrax and combined AV7909 groups).

The Per Protocol (PP) Population will include participants who are randomized and do not have any of the deviations listed below:

- History of previous anthrax disease, anthrax exposure, or anthrax vaccination as per eligibility criteria, as evidenced by a baseline (Day 1 pre-vaccination) TNA NF₅₀ above the limit of detection (LOD).
- Missing or out of window vaccination visit at Study Day 15
- Missing or out of window vaccination visit at Study Day 29 for the BioThrax group
- Administration issue(s) with IP, e.g., incorrect dose of IP at one or more vaccination visits, administration of IP associated with a temperature excursion
- Use of prohibited or restricted medications which may have impacted immune response to vaccination as assessed by the Sponsor (this assessment will be completed prior to database lock)
- Missing immunogenicity data (e.g., sample out-of-window, sample not shipped/received, sample not usable by the immunogenicity lab, sample associated with loss of cold chain) at Day 64

The PP Population will be used for analyses of lot consistency and immunogenicity. Participants will be included in the study group based on the vaccine received.

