7.2.4 Adverse Events of Special Interest (AESI)

Treatment-emergent AESIs determined to be of autoimmune etiology based on decision of the DSMB will be summarized by SOC and PT, listed by individual participant.

The incidence rate of treatment emergent AESIs will be summarized and analysed in the similar manner as described in [Section 7.2.3](#).

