 - If not otherwise specified, mean, geometric mean, standard deviation, median, minimum, maximum, and CI values will be formatted with the same number of decimals found in the raw data.
 - One decimal point or two significant digits (e.g., min 0.032 max 18.0) is presented for TNA NF₅₀.
 -
 - Geometric mean ratio will be formatted with two decimal places.
- P-values will be 2-sided and presented with 2 significant digits, i.e. 0.45, 0.045. P-values less than 0.001 will be presented as “< 0.001”.
- Unless otherwise specified, CIs are two-sided with 95% confidence.
- For numerical variable data summary, align decimal point of each statistics across rows. For 95 CI, align the ‘,’ with the decimal point of above statistics.

	Group 1 (N=xxx)	Group 2 (N=xxx)	Group 3 (N=xxx)
Parameter 1			
n	xx	xx	xx
Mean	xx.x	xx.x	xx.x
SD	xx.xx	xx.xx	xx.xx
Median	xx.x	xx.x	xx.x
Min, Max	xx, xx	xx, x	xx, xx

- For categorical variables, the number and percentage of responses will be presented in the form XX (XX.X), where the percentage is in the parentheses. Percentages will be calculated using a denominator of all participants in a specified analysis population (and present at the analyzed visit in by-visit summaries). The denominator will be specified in a footnote to the tables for clarification where necessary. All percentages will be rounded to one decimal place. Unless otherwise specified, the “N=xx” under each column header will represent the number of participants in that group, and all percentages below will be based on this number. Align count (integer) and first parenthesis across each row. Align decimal place of percentages and zero frequencies (present as 0, no percentage).
- Each level of indentation within a table takes a space of 2 characters.

Group 1 (N=xxx) n (%)	Group 2 (N=xxx) n (%)	Group 3 (N=xxx) n (%)
xx (100.0)	xx (100.0)	xx (100.0)
0	xx (xx.x)	x (x.x)
xx (xx.x)	0	xx (xx.x)
xx (x.x)	x (x.x)	xx (xx.x)
x (x.x)	x (x.x)	0

3. Listing

Convention

- Listings should be

sorted by site, study group, subject numbers and (if applicable) visit day/time or sequence number. Values from repeat tests and unscheduled visits should be presented chronologically with values from scheduled visits.

- In a listing, the subject number should be displayed only once for the subject with multiple records. If a subject's records run into multiple pages, display the subject number once for every page.

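### SAE and AESI incidence to Month 13 is a crude proportion of everyone vaccinated, so unobserved time after withdrawal counts as event-free; a censored supporting estimate would correct a small downward bias

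*SAP*

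**What the plan says.** SAP 2.3.1 defines the primary safety endpoint over a fixed window: "Incidences of SAEs from the time of the first vaccination on Day 1 through the 12-month safety follow-up telephone call following the last vaccination". SAP 7.2.3 names the measure: "The safety outcome measure used for the primary safety analysis is the incidence rate of serious TEAEs". The estimators that follow are not rates over time. They are a proportion per group, "The within-group proportion of participants with serious TEAEs and associated two-sided 95% CI (exact Clopper-Pearson confidence limits) will be provided", and a relative risk defined as a ratio of those proportions, "with exact unconditional 95% CI will be provided for treatment comparison between the two groups". No hypothesis is tested.

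SAP 7.2.4 carries the method over to AESIs: "The incidence rate of treatment emergent AESIs will be summarized and analysed in the similar manner as described in" Section 7.2.3.

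Two other places fix the denominator. SAP 3.2 states: "The Safety Population will include all randomized participants who receive at least one vaccination". It sets no follow-up requirement. SAP Appendix I, under table conventions, states: "Percentages will be calculated using a denominator of all participants in a specified analysis population". The limit to participants present at the visit applies there only to by-visit summaries. SAP 4.4 bases descriptive safety presentations on observed cases and imputes nothing except partial or missing dates. SAP 7.2.1 counts any AE starting on or after the first vaccination date as treatment-emergent.

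The sample-size text (SAP 2.4, Protocol 10.1) makes an allowance for loss: "Allowing a 10% drop-out rate, this sample size for safety (3000) is sufficient to detect, with 95% probability, an AE rate of 1:1000". Neither document plans a person-time, time-to-event or completer-based summary of SAEs or AESIs.

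**The concern.** A proportion over a 13-month window is unbiased for the 13-month risk only if everyone is observed to the end or has the event first. A participant who leaves at Month 4 without an SAE stays in the denominator for the whole window and cannot contribute a later event. The printed proportion therefore estimates something below the Month 13 risk, and its exact interval is centred too low.

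This matters most for late events. Protocol 2.3.2 and 8.1.8 justify the long follow-up by possible delayed onset of autoimmune disease. Early loss removes exactly that part of the window, and the planned estimator does not show it. If retention differed between arms, the relative risk would also move, in favour of the arm with more loss.

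**Working it through.** **Inputs from the documents.** AV7909 N = 3300, BioThrax N = 550, planning drop-out 10% (stated for the AV7909 total), safety n = 3000, detectable rate 0.1% with 95% probability (SAP 2.4). Month 13 is Day 394 and the last clinic visit is Day 64 (Protocol 8.1).

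**Assumptions.** True Month 13 SAE risk R of 1% to 3%; constant hazard; loss uniform over either 394 or 64 days; leavers have the same underlying risk as stayers; 10% loss in BioThrax as well. The documents give none of these.

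**Step 1: the plan's own figure.** P(at least one event) = 1 − (1 − 0.001)^n.
- n = 3000: 95.03%, which reproduces the stated 95%.
- n = 3300 × 0.9 = 2970: 94.88%.
- n = 3300, no loss: 96.32%.
- N = 3300 with 10% uniform loss (observable rate 0.095%): 95.66%.

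The detection claim stands whichever way drop-out is treated.

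**Step 2: bias in the proportion.** Daily hazard h = −ln(1 − R)/394. A leaver whose exit is uniform over 0 to a days has mean observed risk m = 1 − (1 − e^(−ha))/(ha). The crude proportion is expected to be 0.9R + 0.1m, so the shortfall is 0.1 × (R − m). SE = √(R(1 − R)/3300).

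| R | m, a = 394 | m, a = 64 | Shortfall, uniform | Shortfall, before Day 64 | SE (AV7909) | Shortfall in SE |
|---|---|---|---|---|---|---|
| 1% | 0.501% | 0.082% | 0.050 points | 0.092 points | 0.173 points | 0.29 / 0.53 |
| 1.5% | 0.752% | 0.123% | 0.075 | 0.138 | 0.212 | 0.35 / 0.65 |
| 3% | 1.508% | 0.247% | 0.149 | 0.275 | 0.297 | 0.50 / 0.93 |

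In relative terms this is about 5% (uniform) or 9% (before Day 64). If all leave just after Day 1, m = 0 and the crude value is 0.9R, a 10% shortfall. That limit needs no constant hazard, only equal risk in leavers and stayers. For BioThrax (N = 550) the same shortfalls are 0.12 to 0.38 SE.

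**Step 3: zero events.** The two-sided 95% upper limit is 1 − 0.025^(1/n): 0.112% for n = 3300 and 0.123% for n = 3000. Under uniform loss the effective n is about 3300 × 0.95 = 3135, and the limit is 0.118%.

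**Step 4: relative risk, true value 1.** Crude ratio = [(1 − dA)R + dA·m] / [(1 − dB)R + dB·m], where dA and dB are the loss fractions on AV7909 and BioThrax.
- dA = dB: ratio 1.00.
- 15% v 5% (assumed): 0.949 uniform, 0.904 before Day 64, and 0.85/0.95 = 0.895 if all at Day 1.
- 5% v 15% (assumed): 1.05 uniform to 1.12 at Day 1.

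The SE of log RR is √((1 − R)/(3300R) + (1 − R)/(550R)), which is 0.458 at R = 1% and 0.262 at R = 3%. The 95% interval thus spans a factor of about 2.5 to 1.7 each way. The assumed 15% v 5% imbalance (uniform or before Day 64) shifts log RR by 0.11 to 0.39 SE.

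**The case against.** The strongest reply is that the plan is conventional and the effect small. Protocol 10.6.2 itself specifies proportions and relative risks without testing, and the SAP follows it. Every scenario for AV7909 lies below one SE. Retention is protected: participants who stop vaccination are encouraged to stay in follow-up (Protocol 7.3, 7.3.1), and a missed interim call does not end contact (Protocol 8.1.8). SAP 5.1 already tabulates withdrawals before the 12-month follow-up ends, and SAP Appendix IV refers to 12-month follow-up completers. All of this stands and limits the point. It does not supply an estimate that allows for incomplete follow-up.

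Several stronger readings are tempting but not supported:
- **That drop-outs are scored as event-free.** Under SAP 7.2.1 an SAE recorded before leaving counts. Only the later, unobserved time is treated as event-free.
- **That no scoring convention exists.** One can be read from SAP 4.4 and Appendix I together.
- **That the analysis keeps the same people the sample-size section removes.** The 10% is not defined. It may include randomized but unvaccinated participants, who never enter the Safety Population. It is stated only for AV7909, so applying it to BioThrax is an extrapolation.
- **That phase 2 shows retention will differ.** The 11.4% (5/44) in Arm 1 of EBS.AVA.208, against none on AVA, is stopping product because of an AE. It is not loss to follow-up, and this protocol keeps such participants under observation.

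**Conclusion.** The point holds as a modest estimation issue. SAP 7.2.3 and 7.2.4 name an incidence rate to Month 13 but estimate a crude proportion in which unobserved time after withdrawal is event-free. With 10% loss the proportion is low by about 5% relative if loss is uniform and at most 10% if it is very early. For an assumed risk of 1% to 3%, that is 0.05 to 0.15 points (uniform) or 0.09 to 0.28 points (before Day 64). These sizes rest on the assumed risk and timing of loss, a constant hazard, and leavers being at the same risk as stayers. If higher-risk participants leave more often, the shortfall could be larger, and simple censoring would not fully repair it.

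A reader might infer that the AV7909 v BioThrax comparison is biased. With equal loss it is essentially unchanged. A shift of about 5% to 10% needs an imbalance such as 15% v 5%, and the documents give no evidence of one. A reader might also infer that the safety sample size is undermined; it is not. No success criterion depends on these estimates. Priority: consider.

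**What to change.** Keep the crude proportions and the relative risk as planned. In SAP 7.2.3 and 7.2.4 add one or both of the following as a supporting analysis by arm:
- cumulative incidence of first serious TEAE and first AESI at Day 394, censored at last contact. A death is itself an SAE; for AESI it should be treated as a competing event.
- the exposure-adjusted rate of first serious TEAE and first AESI per 100 person-years, from first vaccination to event or last contact, with a 95% CI.

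State that both assume non-informative drop-out, and that the rate also assumes a constant hazard. Show the 12-month completer count per arm beside the SAE and AESI tables. Footnote the crude proportion to say that follow-up time after withdrawal is treated as event-free; a note that drop-outs are event-free would be wrong. Align the incidence-rate wording in 7.2.3 and 7.2.4 with the estimator, and say in SAP 2.4 what the 10% covers.

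The cost is SAP wording and one or two extra tables, plus the added assumptions. AE start dates and date of last contact are already used in SAP 4.4, so no new data are needed.
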